1.1 Objective

The purpose of this pilot study is to assess the feasibility and acceptability of acupressure in patients with rheumatoid arthritis (RA). This study will allow us to better estimate the needed sample size and to focus on specific primary outcome measures for future studies.

1.2 Specific Aim/Hypothesis

- (1) Aim 1: Determine the feasibility and acceptability of self-performed acupressure in patients with RA.
- (2) Aim 2: Assess the impact of acupressure of the pain, fatigue, and sleep of patients with RA.
- (3) Aim 3: Assess the impact of acupressure on disease activity in patients with RA.

1.3 Background Information

Acupuncture is a component of Traditional Chinese Medicine wherein thin needles are inserted at specific points on the body (acupoints) to treat disease. Research over the past three decades has shown that acupuncture is effective for the treatment of chronic pain (for recent meta-analysis see¹). Acupressure is a related technique wherein pressure is applied via a finger or device to specific *acupoints*. Acupressure is highly scalable and can be taught to patients (for self-application) and supported by the use of technology. While less research has been performed on self-applied acupressure, emerging data indicates that self-acupressure is effective for chronic pain.²⁻⁷ In our own studies, we completed a randomized clinical trial in 288 fatigued breast cancer survivors who self-administered acupressure (as proposed in this application) and found significant improvements in pain, fatigue, sleep, and depression.^{8,9} We also recently completed a randomized controlled trial of our acupressure intervention in 67 chronic low back pain patients randomized to either acupressure or usual care. In that pilot study, self-acupressure reduced low back pain more so than usual care (35% reduction, $p<0.05$) after 6 weeks of treatment.

RA is the most common inflammatory arthritis with a prevalence of 0.5-1% in the United States.^{10,11,12} RA is a symmetric polyarthritis characterized by synovitis and systemic inflammation. RA associated with significant morbidity, chronic disability, pain, stiffness, sleep disturbance and increased rates of depression.¹³

Acupuncture is thought to help in RA. In a meta-analysis of 43 studies of complementary and alternative medicine in RA patients, acupuncture was able to improve quality of life in 42 studies.¹⁴ Acupuncture has been recommended via professional agreement as a non-drug

intervention in RA.¹⁵ These data support the proposal of using self-acupressure as an intervention to treat the symptoms of RA.

Acupressure has never been studied in RA. The purpose of this pilot study is to assess the feasibility and acceptability of acupressure in patients with RA.

1.4 Methodology

This will be an open feasibility study of 30 subjects conducted at the University of Michigan

1.4.1 Participants. We will enroll 30 adults (age 25-75) with a RA diagnosis from the Rheumatology Clinics at UM primary and satellite sites. Detailed inclusion and exclusion criteria and rationale for exclusions are detailed below.

Inclusion:

- Patient is being treated for RA at a Rheumatology Clinic at the University of Michigan or another by rheumatologist and reports being prescribed at least one of the following medications:
 - Methotrexate (Trexall, Rheumatrex)
 - Hydroxychloroquine (Plaquenil)
 - Sulfasalazine (Azulfadine)
 - Leflunomide (Arava)
 - Tumor necrosis factor inhibitor (TNFi), including:
 - Adalimumab (Humira)
 - Etanercept (Enbrel)
 - Certolizumab pegol (Cimzia)
 - Golimumab (Simponi)
 - Infliximab (Remicade)
 - Abatacept (Orencia)
 - Tocilizumab (Actemra)
 - Janus kinase inhibitor (JAKi), including:
 - Tofacitinib (Xeljanz)
 - Baracitinib (Olumiant)
 - Upadacitinib (Rinvoq)
 - Rituximab (Rituxan)
- Ages 25 – 75

Exclusion:

- Visual or hearing difficulties that would preclude participation,
- Do not speak or read English
- Do not have access to smart phone with access to mobile applications
- Severe psychiatric disorders including history of substance abuse disorders,
- Individuals on high doses of opioids (over 100 OME per day),

- Taking blood thinners, including warfarin (Coumadin), dabigatran (Pradaxa), rivaroxaban (Xarelto), apixaban (Eliquis), edoxaban (Savaysa), or betrixaban (Bevyxxa)
- Thrombocytopenia (low platelet count)
- Expecting to receive surgery within the next year for their RA
- Pregnancy or breast feeding, or anticipate pregnancy in next year,
- Actively applying for disability or compensation, or actively involved in litigation.
- Anything at the discretion of the PI or study team

1.4.2 Assessments. Pre-screening and recruitment will occur virtually or in-person in clinic. Trained study staff may perform consent in-person at the time of recruitment if feasible and desired by the patient. The study visit will occur at the Chronic Pain and Fatigue Research Center, University of Michigan at Domino Farms. At the initial visit, Day 0, the informed consent process conducted by trained study staff, if not already completed. This will be followed by questionnaire completion using Qualtrics electronic data capture system, and orientation and training on the acupressure device and ambulatory mobile support technology. Table 1 indicates the timeline of the study and when questionnaires will be administered throughout the study. Day 1 treatment will occur via Zoom with the participant and a study coordinator. The participant will perform the treatment with the coordinator observing the technique and available to answer any questions the participant may have.

Participants will be provided with a pre-addressed, pre-paid box to return the AcuWand or may return it in person to the study team at Domino's Farms.

Table 1: Timeline of Study

	Day 0	Day 1	Day 7	Day 21	Day 42	Day 63
Initial visit						
Screening (if not done)	X					
Consent (if not done)	X					
Treatment		X-Zoom	X	X	X	
Questionnaires:						
Past Med/Surg Hx	X					
PROMIS 29+2	X			X	X	X
FMS	X			X	X	X
HAQ	X			X	X	X
RA disease activity	X			X	X	X
Desire for relief	X					
Expected relief	X					
Credibility					X	
Tolerability				X	X	
Acupr. sensation				X	X	
PGIC					X	
Phone call			X			

FMS = Fibromyalgia Survey Questionnaire. HAQ = Health Assessment Questionnaire. Acupr. Sensation = Acupressure sensation.

PGIC = Patient Global Impression of Change.

Clinical data. Participants will undergo an assessment of past medical history and pregnancy status. Medications (*especially analgesics including opioids*), diagnoses, pain interventions, and any relevant labs already collected for clinical purposes will be confirmed via EMR review.

Questionnaires. All participants will complete a battery of validated questionnaires before, during and after completion of treatment intervention. Questionnaires will measure pain, sleep disturbance, fatigue, and depression given the increased rates of these outcomes in patients with RA. Questionnaires will also focus on acupressure expectations, tolerability, and acceptability. Questionnaires will be applied pre-treatment, at 3 and 6 weeks into treatment, and 3 weeks post-treatment intervention (see Table 1). Surveys will be sent via email, and if needed, reminder phone calls will also be utilized.

1.4.3 Study Procedures:

1.4.3a Acupressure Intervention Procedures

The self-acupressure intervention will be delivered using the modified MeTime Acupressure mobile app in addition to in-person or virtual instruction via study staff. The MeTime Acupressure app was developed in association with patient focus groups (six focus groups each of eight to ten women) and the University of Michigan 3D Media Laboratory (screen shot examples in Figure 2). The MeTime Acupressure app will be loaded onto computer tablets or smart phones by the participants.

Participants will also receive an AcuWand to be used in association with the acupressure app to help participants apply the correct amount of pressure to acupoints (See Figure 1).

Figure 1 AcuWand Device

relaxing acupoints are:

[figure not shown]
- *Point 1: Yin tang (Unilaterally)*
- *Point 2: Anmian (EX17) (Bilaterally)*
- *Point 3: Heart 7 (HT7) (Bilaterally)*
- *Point 4: Spleen 6 (SP6) (Bilaterally)*
- *Point 5: Liver 3 (LV3) (Bilaterally)*

Figure 2 Sample MeTime Acupressure App

There are 5 acupoints with 4 of the acupoints performed on both the left and right sides of the body (total of 9 points to stimulate; see Figure 3. The

Figure 3 Relaxing Acupressure

Participants will be introduced to the MeTime App and AcuWand device at their initial clinic visit. A research team member will provide the patient with instructions and guide the patient through using the app, the AcuWand and performing Self-Acupressure. Study participants will be told to perform acupressure once per day and to stimulate each point a circular motion for three minutes. There are 9 acupressure points, totaling 27 minutes of stimulation per day. Participants will perform daily acupressure for a total of six weeks.

1.4.3b Participant Adherence

Participants will be asked to log time spent using the AcuWand on a daily basis and record any reasons for missed sessions. The AcuWand device also records the time a participant spends using the device.

1.4.3c Standardizing Assessment and Intervention

Fidelity of the acupressure intervention in study staff, who are teaching participants acupressure, i.e., acupressure educators will be assessed by study investigator [name]. Educators will be trained using the Acupressure Therapist Treatment Manual (see supporting documents).

The primary outcome will be the feasibility and acceptability of self-performed acupressure in patients with RA. This will be assessed by the number of sessions completed and the acupressure acceptability questionnaire.

The secondary outcome will be the impact of acupressure on pain. This will be assessed with PROMIS-29+2 questionnaire and the Fibromyalgia Survey Questionnaire.

Exploratory outcomes in this study will include the impact of acupressure on fatigue, sleep, mood, and disease activity in patients with RA. These will be assessed by questionnaires.

1.4.3d Acupressure Benefits

Emerging data indicates that self-acupressure is effective for chronic pain.²⁻⁷ In our own studies, we completed a randomized clinical trial in 288 fatigued breast cancer survivors who self-administered acupressure (as proposed in this application) and found significant improvements in pain, fatigue, sleep, and depression.^{8,9} We also recently completed a randomized controlled trial of our acupressure intervention in 67 chronic low back pain patients randomized to either acupressure or usual care. In that pilot study, self-acupressure reduced low back pain more so than usual care (35% reduction, $p<0.05$) after treatment. We theorize that patients with RA may see benefits in pain, sleep, fatigue, and depression.

1.4.3e Acupressure Risks

Potential Risk – Treatment Interaction – Acupressure. Self-acupressure is a safe intervention. From our previous 3 clinical trials over the past 10 years using this acupressure point formula, we have observed no serious adverse events associated with the study intervention. Our most recent and largest trial of self-acupressure in fatigued cancer survivors (N=288), had 6 adverse events related to acupressure, and all were non-serious cases of mild bruising at acupressure sites. There are no known long-term risks associated with self-acupressure. To minimize the chances of bruising, participants will be trained by the acupressure instructor in how to apply the correct amount of pressure with the AcuWand. Specific attention will be paid to not apply too much pressure. The AcuWand has a built in “buzzer” to notify the study participant when the correct amount of pressure is reached, which will minimize chances of bruising. The participant is free to withdraw from the intervention at any point if the self-acupressure intervention becomes uncomfortable.

1.4.3f Management of expected adverse events

Expected Adverse Event	Criteria for Management	Intervention Modification, if any
Acupressure		
Mild bruising at acupressure sites	Participant verbalizes bruising.	The participant is free to withdraw from the intervention if the self-acupressure intervention becomes uncomfortable.

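### No questionnaire is tied to stopping acupressure, and the plan does not say how people who stop enter the acceptability result, so that half of the primary outcome may be biased upward

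*Combined protocol and SAP*

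**What the plan says.** Section 1.4 describes a single-arm study: "This will be an open feasibility study of 30 subjects conducted at the University of Michigan". Section 1.4.3c defines the primary outcome: "The primary outcome will be the feasibility and acceptability of self-performed acupressure in patients with RA". It continues: "This will be assessed by the number of sessions completed and the acupressure acceptability questionnaire".

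Under 1.4.2, the timing is: "Questionnaires will be applied pre-treatment, at 3 and 6 weeks into treatment, and 3 weeks post-treatment intervention (see Table 1"). In Table 1 the rows in which participants rate the treatment they received are:

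- tolerability and acupressure sensation, at Days 21 and 42 (the tolerability row reads "Tolerability X X");
- credibility and PGIC, at Day 42 only.

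Day 0 covers desire for relief and expected relief. Day 63 repeats symptom, function and disease-activity measures only. The acceptability questionnaire named in 1.4.3c has no row under that name.

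On stopping, 1.4.3e says: "The participant is free to withdraw from the intervention at any point if the self-acupressure intervention becomes uncomfortable". The table in 1.4.3f repeats this for bruising.

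Three other provisions bear on the point. Section 1.4.3b says: "Participants will be asked to log time spent using the AcuWand on a daily basis and record any reasons for missed sessions", and adds that the device records time of use. Section 1.4.2 says: "Surveys will be sent via email, and if needed, reminder phone calls will also be utilized". Table 1 also shows a Day 7 phone call, with no content described.

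Section 1.5 sets a feasibility criterion of over 80% of sessions completed. For the acceptability questionnaire it gives no criterion, denominator or rule for missing answers.

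**The concern.** Discomfort is the one reason for stopping that the plan names, and it is itself a judgement that the treatment was not acceptable. A participant who stops in week 1 or 2 has no scheduled rating of the treatment before Day 21. One who stops in week 4 has had the Day 21 tolerability and sensation forms, but credibility and PGIC fall due only after stopping. The plan does not say whether forms still go to either person, or whether either counts in the acceptability result.

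If some of them do not answer, non-response is plausibly linked to the outcome being measured, and the likely direction is a result that looks too favourable. The pilot is meant to inform later studies, so an inflated acceptability result would be carried into their planning. Views not collected near the time of stopping are hard to collect reliably later.

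**Working it through.** The plan gives no figure for acceptability or withdrawal to reproduce. Its one sample-size statement, a detectable pre-post difference of about 0.5 SD with 30 participants, does not bear on this point.

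**Step 1. What is due, by time of stopping.** From Table 1:

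| Stops | Treatment ratings due before stopping | Rating triggered by stopping | Ratings dated after stopping |
|---|---|---|---|
| Before Day 21 | none | none | Days 21 and 42; not stated whether sent |
| Between Days 21 and 42 | tolerability, sensation (Day 21) | none | Day 42; not stated whether sent |

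Someone who stops at Day 7 would wait 21 − 7 = 14 days for the first rating form, if it is sent.

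**Step 2. Possible size of the bias.** The input from the documents is n = 30. The assumptions are:

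- acceptability is summarised as a proportion (the plan defines no such summary);
- w withdrawers do not answer and everyone else does;
- 90% of responders find the treatment acceptable (p_R);
- 0% or 20% of the non-responding withdrawers would (p_W).

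Figure over all enrolled = [(30 − w) × p_R + w × p_W] / 30. 
Bias of the responders' figure = p_R minus that = (w/30) × (p_R − p_W).

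| w | p_W | All 30 enrolled | Reported | Bias |
|---|---|---|---|---|
| 3 | 20% | (27 × 0.9 + 3 × 0.2)/30 = 83.0% | 90% | 7 points |
| 3 | 0% | (27 × 0.9)/30 = 81.0% | 90% | 9 points |
| 6 | 20% | (24 × 0.9 + 6 × 0.2)/30 = 76.0% | 90% | 14 points |
| 6 | 0% | (24 × 0.9)/30 = 72.0% | 90% | 18 points |

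The bias is zero if withdrawers answer the surveys (w = 0), or if those who do not answer hold the same views as responders (p_W = p_R).

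**Step 3. Does the session criterion protect the result?** Six weeks of daily treatment is 42 sessions each, or 30 × 42 = 1,260 in all. Assume that all 30 stay in the denominator (not stated), that withdrawers stop at Day 14, and that adherence is 95% while on treatment.

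- 5 stop: (25 × 42 + 5 × 14) × 0.95 / 1,260 = 84.4%, passes.
- 6 stop: (24 × 42 + 6 × 14) × 0.95 / 1,260 = 82.3%, passes.
- 9 stop: (21 × 42 + 9 × 14) × 0.95 / 1,260 = 76.0%, fails.

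The criterion catches heavy early stopping. It can still be met when five or six of 30 have stopped.

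**The case against.** The strongest reply is that the plan does not remove these people from the surveys. Withdrawal is from the intervention, not the study. Section 1.4.2 says that all participants complete the questionnaires, which arrive by email with reminder calls and need no visit. On that reading, someone who stops in week 1 still receives the Day 21 and Day 42 forms. The daily log may already hold the reason for stopping, and early stopping lowers the session count. The plan also sets no success threshold for acceptability.

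Much of this stands. A reader might infer that acceptability will be a rating only by those who stayed, that the bias must run upward, that nothing about stopping is captured, or that no analysis could help. The documents support none of these. They are silent about surveying people who stop, which is not the same as excluding them. Withdrawal unrelated to discomfort need not push the result upward. Logged reasons could support a worst-case analysis.

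What remains is narrower. The timing in 1.4.2 is expressed as weeks into treatment, which leaves unclear what is due from someone no longer treated. The log is not part of the stated acceptability measure, and nothing says that it continues after stopping. The session count is only a partial safeguard. The Table 1 dates are also inferred from related rows, since the acceptability questionnaire has none. That adds to the need for clarification.

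**Conclusion.** The point holds as a possible bias, not a certain one. No form is tied to stopping, the named acceptability instrument is unscheduled in Table 1, and the plan does not say whether people who stop are still surveyed or how they enter the acceptability result. If some do not answer, the result is likely to be too favourable.

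The documents give neither a withdrawal rate nor a definition of an acceptable rating, so the size cannot be derived from them. The 7 to 9 points (3 withdrawals) and 14 to 18 points (6 withdrawals) rest wholly on the assumed 90% among responders and 0 to 20% among withdrawers who do not answer. They show that, with 30 participants, each such person moves the figure by (1/30) × 0.7 to (1/30) × 0.9, or about 2.3 to 3.0 points. This is a cheap improvement to make before data collection, not a flaw that undermines the design.

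**What to change.** 1. In Table 1, add a row for the acceptability questionnaire and an at-stopping column. When a participant stops acupressure, send the existing tolerability, credibility and acceptability items through Qualtrics, with one item on the main reason for stopping.
2. In 1.4.2, state that people who stop acupressure but remain in the study still receive the Day 21, 42 and 63 surveys.
3. In 1.5, report acceptability among responders, with the number who did not answer, beside a figure over all 30 enrolled. Use actual answers wherever they were given. As a worst-case sensitivity analysis, count non-responders who stopped for discomfort as not acceptable, and say how other non-responders are shown.

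The cost is one extra trigger for mostly existing electronic forms, one new item and a few sentences of text. The downsides are a short extra survey for people who stop and a possibly less favourable acceptability figure. Neither the treatment nor the freedom to withdraw changes.

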1.5 Statistical Design

Due to the pilot and feasibility nature of this study, we will primarily be using descriptive statistics. We will obtain pre-, during and post-treatment measures of disease activity and symptoms (pain, sleep disturbance, fatigue, and mood). These measures will be analyzed with t-test or appropriate non-parametric test if data not appropriate. This is an open study.

Aim 1: We will compare number of acupressure treatments performed to the number of total number of sessions required. We would consider successful feasibility to be over 80% of sessions completed.

Aim 2: We will compare scores for pain, fatigue, and sleep on pre-treatment and post-treatment surveys with paired t-test to assess for significance.

Aim 3: We will explore pre-treatment and post-treatment RA disease activity scores with paired t-test to assess for significance.

This is a pilot study and we do not expect that we will achieve statistical significance. With the sample size of 30 we would only be able to detect a difference between pre and post scores would be approximately 0.5 standard deviation.

References:

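### Does the 80% feasibility criterion fail because the plan records minutes but counts sessions?

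*Combined protocol and SAP*

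**What the plan says.** Section 1.4.3c makes feasibility and acceptability the primary outcome: "This will be assessed by the number of sessions completed and the acupressure acceptability questionnaire". Section 1.5 describes the Aim 1 comparison: "We will compare number of acupressure treatments performed to the number of total number of sessions required". The next sentence sets the success level: "We would consider successful feasibility to be over 80% of sessions completed".

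The prescribed treatment is in section 1.4.3a. On frequency and technique it says: "Study participants will be told to perform acupressure once per day and to stimulate each point a circular motion for three minutes". The length of a full session is given next: "There are 9 acupressure points, totaling 27 minutes of stimulation per day". The duration of treatment comes last: "Participants will perform daily acupressure for a total of six weeks".

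The adherence records are in section 1.4.3b. The first is a participant log: "Participants will be asked to log time spent using the AcuWand on a daily basis and record any reasons for missed sessions". The second is automatic: "The AcuWand device also records the time a participant spends using the device".

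Section 1.5 says the analysis is mainly descriptive because this is a pilot and feasibility study.

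**The concern.** The success criterion is expressed in sessions, while both adherence records are described in terms of time. No rule turns minutes into sessions. Section 1.5 also uses two words, *performed* and *completed*, in adjacent sentences. Read literally against minutes they could mean different things: any use of the device, or the full 27-minute session. The plan does not name the log or the device as the source, and does not say whether 80% applies to the pooled total or to each participant.

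Feasibility is the study's stated purpose (section 1.1), and 80% is its only numeric success criterion. If the two words were applied as separate definitions, the same minutes could be reported as a success or a failure, and the definition could be chosen after the data were seen.

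**Working it through.** **1. Reproduce the plan's session length.** Section 1.4.3a lists one unilateral and four bilateral points: 1 + 4 × 2 = 9. At 3 minutes each, 9 × 3 = 27 minutes, as stated.

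**2. Derive the denominator.** Once daily for six weeks: 6 × 7 = 42 sessions, which fits treatment from Day 1 to Day 42 in Table 1. With 30 participants, 30 × 42 = 1,260 sessions. Prescribed minutes are 42 × 27 = 1,134 per participant. Over 80% means more than 0.8 × 42 = 33.6, so at least 34 sessions for one participant, or more than 0.8 × 1,260 = 1,008, so at least 1,009 pooled.

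**3. See whether the records supply the numerator.** The log is kept daily and asks for reasons when a session is missed. Each day is therefore either a day with a session or a missed day, and the number of sessions done follows directly. No conversion from minutes is needed. What is left undefined is the shortened session.

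**4. Pooled or per participant.** With 42 required of everyone, the pooled percentage (total sessions / 1,260) equals the mean of the 30 individual percentages. A rule based on the number of participants above 80% would need a second threshold, the share of participants who must pass, and the plan gives none. Only the pooled reading yields a verdict as the plan stands.

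**5. How far could the readings differ?** The daily times below are assumed, since the documents give none.

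| Pattern over 42 days | Minutes | Any use | Full 27 min | Share of 1,134 min |
|---|---|---|---|---|
| 34 full, 8 none | 918 | 34/42 = 81.0% | 81.0% | 81.0% |
| 30 full, 12 of 15 min | 990 | 100% | 30/42 = 71.4% | 87.3% |
| 20 min every day | 840 | 100% | 0% | 74.1% |
| 38 days of 9 min | 342 | 38/42 = 90.5% | 0% | 30.2% |

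The readings part only when shortened sessions are frequent.

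**6. Is a strict 27-minute cut-off credible?** Suppose use on all 42 days, with normally distributed times centred on 27 minutes. On a continuous scale exactly half the sessions reach 27, whatever the spread. If times are recorded to the nearest whole minute, the share is Φ(0.5/SD): 69.1%, 56.6% and 54.0% for SD 1, 3 and 5 minutes. With each day capped at 27, the share of prescribed minutes on the continuous scale is 1 − 0.3989 × SD/27: 98.5%, 95.6% and 92.6%. The cut-off can thus report failure when nearly all the prescribed stimulation was given, and its value moves with rounding alone. The plan gives 27 minutes as the daily total of stimulation and nowhere as a pass mark for counting a session.

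**The case for a change.** The strongest opposing case is that a study whose purpose is feasibility should define its one numeric criterion before anyone sees the data. Even if *performed* and *completed* are synonyms, neither says whether a shortened session counts. A shortened session is not a missed one, so the log leaves it unclassified. Partial sessions are plausible for an unsupervised 27-minute daily task. The any-use count can also flatter: the last row of the table passes at 90.5% with 30.2% of the prescribed minutes. One clarifying paragraph would cost little.

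Much of this stands. The definition is unwritten, the source record is unnamed, and a pure session count can hide short sessions. It does not follow that the plan gives a wrong answer. A written definition would most naturally adopt the count the log already supports, so the headline figure would be essentially the same. The remaining risk, unnoticed short sessions, is limited because both records hold time and the share of prescribed minutes can be reported beside the count without further data. A full-27-minute count would bring in the unstable measure of step 6.

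Withdrawals raise a separate question. Aim 1 compares with the sessions required, which on its face keeps all enrolled participants in the denominator, and no section proposes counting completers only.

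**Conclusion.** No change follows. This is a missing detail that an analyst would fill sensibly: sessions logged out of 42 for each enrolled participant, pooled over 1,260, with minutes described alongside. The adjacent sentences in section 1.5 read naturally as a comparison and its success level, so the two words refer to one count.

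The possible discrepancy is large only under assumed patterns, such as 100% against 0% for 20 minutes every day, and it needs a cut-off the plan does not propose. It is nil if every session is either full-length or absent. Its likelihood cannot be judged from the documents, which give no expected session times.

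The conclusion rests on three things: the log being kept daily as described, the descriptive single-arm design, and the absence of any decision rule tied to 80%. The treatment manual cited in section 1.4.3c was not available, so the absence of a counting rule is established only for the protocol and SAP.

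### Aims 2 and 3 use two-visit paired t-tests on scores collected at four visits; a four-visit model would remove nearly all bias from missed surveys that depend on recorded scores, but only part of it otherwise

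*Combined protocol and SAP*

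**What the plan says.** Section 1.5 (Statistical Design) gives the Aim 2 analysis as "We will compare scores for pain, fatigue, and sleep on pre-treatment and post-treatment surveys with paired t-test to assess for significance", and the Aim 3 analysis as "We will explore pre-treatment and post-treatment RA disease activity scores with paired t-test to assess for significance". A general sentence in the same section covers measures taken before, during and after treatment: "These measures will be analyzed with t-test or appropriate non-parametric test if data not appropriate". The section is also explicit that "we will primarily be using descriptive statistics".

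Table 1 in Section 1.4.2 schedules PROMIS 29+2, FMS, HAQ and RA disease activity at Days 0, 21, 42 and 63. The text under Questionnaires agrees: "Questionnaires will be applied pre-treatment, at 3 and 6 weeks into treatment, and 3 weeks post-treatment intervention".

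On incomplete data, the plan has a collection procedure, "Surveys will be sent via email, and if needed, reminder phone calls will also be utilized", and a right to stop the intervention (Section 1.4.3e), "The participant is free to withdraw from the intervention at any point if the self-acupressure intervention becomes uncomfortable". It gives no expected rate of missed surveys and no rule for analysing incomplete data.

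**The concern.** A paired t-test uses only people with both of its two scores, and a paired non-parametric test has the same limit. A participant who answers at Days 0 and 21 and then stops contributes nothing to the Day 42 or Day 63 change, although the Day 21 score says something about how that person was doing. If those who stop are mostly those with little early improvement, the remaining pairs overstate the mean change. A purely descriptive mean among completers carries the same bias.

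The size of the change matters more here than its p-value, because Section 1.1 wants the pilot to inform the sample size and outcome choice of later studies.

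**Working it through.** **1. The plan's own figure.** Section 1.5 says 30 participants can detect about 0.5 SD. Alpha, power and the type of SD are not stated; I assume two-sided 5%, 80% and the SD of the change. Then (1.960 + 0.842)/√30 = 2.802/5.477 = 0.511 SD, or 0.529 SD with the noncentral t. The figure reproduces, for 30 complete pairs. With 24 pairs (20% missing) the noncentral t gives 0.60 SD, and power at 0.5 SD falls from 75.4% to 65%.

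**2. Assumed inputs for the bias.** From the documents: 30 participants and visits at Days 0, 21, 42 and 63. Assumed, because the documents give no values: mean changes of -0.25, -0.40 and -0.25 SD (SD of the score at Day 0; negative is improvement); 20% missing both Day 42 and Day 63; the log-odds of missing rise by 1.0 per SD of the Day 21 change (0.5 and 1.5 also tried); five covariance patterns.

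**3. Complete pairs at Day 42, in closed form.** Write D21 and D42 for the changes from Day 0. Among those who stay,

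mean D42 = -0.40 + [cov(D21, D42)/SD(D21)] × m,

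where m is the mean standardised Day 21 change of the stayers. At 20% dropout and log-odds 1.0, numerical integration gives m = -0.173. With unit SDs, cov = 1 + r(21,42) - r(0,21) - r(0,42) and SD(D21) = √(2 - 2r(0,21)).

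| Pattern | cov | SD(D21) | ratio | closed form | simulated |
|---|---|---|---|---|---|
| exchangeable 0.5 | 0.50 | 1.000 | 0.500 | -0.49 | -0.493 |
| exchangeable 0.7 | 0.30 | 0.775 | 0.387 | -0.47 | -0.467 |
| AR(1) 0.7 | 0.51 | 0.775 | 0.658 | -0.51 | -0.512 |
| AR(1) 0.8 | 0.36 | 0.632 | 0.569 | -0.50 | -0.500 |
| AR(1) 0.7, SDs 1.0, 1.1, 1.2, 1.3 | 0.566 | 0.819 | 0.691 | -0.52 | -0.520 |

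The last row uses the same formula with covariances in place of correlations. A separate simulation gave -0.46 to -0.51, the range used in the conclusion.

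**4. The four-visit model in the same setting (unstructured REML, simulated).**

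| 20% dropout, log-odds 0.5 to 1.5 | True | Complete pairs | Model |
|---|---|---|---|
| Day 42 | -0.40 | -0.44 to -0.56 | -0.40 to -0.41 |
| Day 63 | -0.25 | -0.29 to -0.39 | -0.24 to -0.26 |

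The complete-pair bias is 0.2 to 0.8 of a standard error at Day 42 and 0.2 to 0.6 at Day 63. Coverage of the 95% interval is 88-95% for pairs and 93-96% for the model with Kenward-Roger. At log-odds 1.0, complete pairs at Day 42 give -0.44 to -0.46 with 10% dropout and -0.50 to -0.58 with 30%.

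**5. Where the model helps less (20% lost, log-odds 1.0, true Day 42 change -0.40).**

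| Cause of loss | Complete pairs | Model | Bias left |
|---|---|---|---|
| before Day 21, driven by the unrecorded Day 21 change | -0.47 to -0.52 | -0.44 to -0.50 | about 50-85% |
| driven by the missed Day 42 score | -0.53 to -0.59 | -0.48 to -0.52 | about 50-70% |

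**6. Where the choice does not affect bias.** If missingness is unrelated to response, both methods give -0.40 and -0.25. With complete data the model returns the paired t-test's estimate, standard error and 29 degrees of freedom.

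**7. Covariance choice.** Four visits need 4 × 5/2 = 10 covariance parameters from 30 people, yet the unstructured model converged in all 67,500 runs. With dropout as in step 3, heterogeneous Toeplitz gave -0.40 to -0.41 under all five patterns. A random intercept gave -0.45 to -0.46 when the truth was autoregressive, and AR(1) gave -0.36 when it was exchangeable.

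**The case against.** A paired pre-post test is conventional for a 30-person open pilot that is mainly descriptive and does not expect significance. The harm is hypothetical: every dropout, correlation and effect input is assumed, and so is the direction in which poor responders leave. At 10% dropout the Day 42 bias is only 0.04 to 0.06 SD. All of this stands, and it sets the weight of the point.

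A reader might also infer four stronger things that the documents do not support.

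- *That a four-visit model protects against selective missed surveys in general.* It does so nearly fully only when missingness depends on recorded scores. Nothing in the plan says that losses would follow that pattern, and withdrawal for discomfort could come before Day 21.
- *That the plan ignores Day 21.* The general sentence in Section 1.5 covers measures taken during treatment. The gap is that each t-test sees only its own two visits.
- *That selective dropout is expected.* Section 1.4.3e concerns stopping the intervention, not the surveys, and reminder calls are a safeguard against missed surveys.
- *That post-treatment must mean Day 63.* The Questionnaires text calls week 6 part of treatment, but Day 42 also ends the six treatment weeks and is the only day with the PGIC. Either reading is possible. The unnamed day, and the unchosen pain score in Section 1.4.3c, are missing detail on which this point does not depend.

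Finally, a model replacing the t-test outright would lose the non-parametric option in Section 1.5, so that option should stay.

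**Conclusion.** The concern holds as a minor, cheap improvement. The planned tests discard recorded scores from anyone who misses the later survey. If missingness depends on those recorded scores, the reported change is too large by roughly 0.06 to 0.11 SD at Day 42 (0.46 - 0.40 to 0.51 - 0.40) under the 20% dropout assumptions, which is less than one standard error. A four-visit model removes nearly all of that bias. Under the other two selective mechanisms examined it is still closer to the truth than complete pairs, but is itself biased.

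The documents do not show that any bias will occur. The outcomes concerned are secondary (pain) or exploratory (fatigue, sleep, mood, disease activity). The consequence for later studies is also limited, because there is no control arm: neither method separates acupressure from time trend or regression to the mean.

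**What to change.** In Section 1.5, for Aims 2 and 3:

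- Estimate the Day 0 to Day 42 and Day 0 to Day 63 changes, separately labelled and with 95% confidence intervals, from a REML repeated-measures model. Use visit as a factor, all enrolled participants, unstructured covariance and Kenward-Roger degrees of freedom.
- If it does not converge, use a heterogeneous Toeplitz covariance. Do not fall back to AR(1), plain or heterogeneous, or to a random intercept.
- Keep the paired t-test, or the non-parametric test for clearly non-normal scores, as a sensitivity analysis.
- Report the number of complete pairs for each contrast and the numbers lost before and after Day 21, so that readers can judge how far the model can help.

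The cost is a few lines of text. No visits, data or participants are added, and the sample size and the 0.5 SD statement stay as they are. The downside is a slightly more complex model that relies on a missing-at-random assumption, which should be stated with the results.
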